Graphically displayed over follow-up times (1, 3, 6 and 12 months) using boxplots containing the median, quartiles and outliers. At each follow-up time point (1,3, 6 and 12 months) we will assess whether 80°C and 90°C RFA temperatures differ with respect to the percentage of pain relief using the Wilcoxon rank-sum test. The significance criterion will be 0.05/4=0.0125 at each time, using a Bonferroni correction to control the type I error at 0.05 for the primary hypothesis. In addition to the P-value, the estimated median percentage of pain relief for each group and difference in medians with confidence intervals will be reported. The estimated probability of pain relief at 90°C being better than at 80°C with confidence interval will be reported, since the Wilcoxon rank sum test has a null hypothesis that this probability is 0.50. All the confidence intervals will be estimated based on bootstrapped standard error with 10,000 bootstrap replications (8).

Interim analyses:

Interim analyses will be conducted for efficacy and futility at each 25% of the maximum enrollment (see Sample Size Considerations) using a group sequential design and gamma spending function (using gamma = -4 for efficacy and -2 for futility). P-value boundaries for efficacy (futility in parentheses) will be P \leq 0.0016 (P>0.957), P \leq 0.0048 (P>0.719), P \leq 0.0147 (P>0.239), and P \leq 0.0440 (P>0.0040) at looks 1 through 4, respectively.

• Secondary hypotheses: We will compare randomized groups on the following variables:

VAS pain scores/Pain Disability Index (PDI)/McGill Pain questionnaire scores/Beck Inventory (BI) scores.

While the detailed description below focuses on the VAS pain score outcome for brevity, the analysis approach will be the same for Pain Disability Index (PDI), McGill Pain questionnaire scores, and Beck Inventory (BI) scores.

Graphical analysis will be undertaken to describe the degree of pain reduction observed in patients undergoing each treatment. The association between RFA temperature and pain reduction will be performed using a mixed effects model adjusting for time interval and also for baseline pain score to increase precision. We will assess the group-time interaction and assess treatment effects at each time if interaction P <0.15. The mixed model will account for potential intra-subject correlation of repeated VAS pain measurements within a patient using a spatial

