correlation structure. A model-based Wald test for regression model coefficients will be used to evaluate whether or not RFA temperature affects mean pain reduction.

Opioid Consumption:

As preliminary retrospective study showed, postoperative opioid consumption is largely binary in nature for this patient's population, as over 60% of our patients did not take any opioids. Thus, postoperative opioid consumption within a year of the first RFA will be analyzed as a binary outcome, i.e., any versus none (however, dosage information among the subset of patients taking any opioids will be described using medians and quartiles for each group). Multivariable logistic regression will be used to estimate the adjusted relative risk for postoperative opioid use comparing patients undergoing RFA at 90°C to patients undergoing RFA at 80°C. A logistic model-based Wald test for regression coefficients will be used to test the hypothesis of the effect of temperature on the postoperative opioids use (i.e., whether or not the relative risk is different from a value of 1.0).

Number of repeat of RFA procedures

Need for repeated RFA procedure over one year period will be analyzed as a count variable using a proportional odds logistic regression model. If the number of repeats greater than 1 is very rare, we will use a binary outcome of any RFA procedure comparing two groups of patients.

Complications:

Incidence of each individual complication will be reported for each group, with confidence intervals. Possible adverse events (persistent paresthesia, nerve injury, bleeding and infection) will be summarized into a single composite binary outcome, i.e., any versus none. The risk of experiencing one or more adverse events will be compared between RFA at 90°C and RFA at 80°C groups using logistic regression.

Type I error will be controlled at 5% for the secondary outcomes using the Bonferroni correction for simultaneous hypotheses. SAS 9.3 software (SAS Institute, Cary, NC) and R statistical software version 2.7.2 (The R Foundation for Statistical Computing, Vienna, Austria) will be used for all analyses and graphics.

Sample size considerations:

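### Naming Holm's step-down procedure instead of single-step Bonferroni for the secondary outcomes would keep the same 5% error control and add power when several effects are real (a cheap improvement, not an error)

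*Combined protocol and SAP*

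**What the plan says.** The rule comes at the end of the secondary analyses in Data Analysis, after the Complications paragraph: "Type I error will be controlled at 5% for the secondary outcomes using the Bonferroni correction for simultaneous hypotheses". It gives neither the number of hypotheses nor a per-test level, and the plan mentions no step-down or hierarchical method for this family.

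The comparisons have to be collected from the text:

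- Four scales under Secondary hypotheses: "VAS pain scores/Pain Disability Index (PDI)/McGill Pain questionnaire scores/Beck Inventory (BI) scores".
- Opioid use: "postoperative opioid consumption within a year of the first RFA will be analyzed as a binary outcome".
- Repeat procedures: "Need for repeated RFA procedure over one year period will be analyzed as a count variable".
- Adverse events, which "will be summarized into a single composite binary outcome, i.e., any versus none" and are compared by logistic regression.

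For the scales there may also be tests by visit: "We will assess the group-time interaction and assess treatment effects at each time if interaction P <0.15".

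The primary outcome has its own, separate correction over the four visits: "The significance criterion will be 0.05/4=0.0125 at each time, using a Bonferroni correction".

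**The concern.** Single-step Bonferroni holds every secondary test to 0.05/m, however many of the others have already been rejected. Holm relaxes the level after each rejection without giving up error control. As a testing rule, Bonferroni is therefore dominated.

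The difference matters only when several null hypotheses are false, and the sponsor expects that. Under Specific Hypotheses (Secondary), 90°C is expected to do better on the four scales, with less opioid use and fewer repeat procedures. What is at stake is how many of those six supporting claims the trial can make if they are true. The primary conclusion and the sample size are not affected.

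**Working it through.** **1. The plan's own figure.** For any m, Bonferroni's error bound is m × (0.05/m) = 0.05, as stated. The primary level, 0.05/4 = 0.0125, is also right.

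**2. Size of the family.** Outcomes Data lists six secondary outcomes, with adverse events under a separate heading. The composite complication test makes seven. If by-visit tests replaced the overall test on each scale, the count would be 4 scales × 4 visits + 3 = 19. The Bonferroni level is then 0.05/6 = 0.0083, 0.05/7 = 0.0071 or 0.05/19 = 0.0026. I use seven as the base case; this is an inference.

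**3. Thresholds for m = 7.** Bonferroni applies 0.00714 to every test. Holm orders the P values and compares them in turn with 0.00714, 0.00833, 0.0100, 0.0125, 0.0167, 0.025 and 0.05, stopping at the first failure. No Holm threshold is below Bonferroni's, so no Bonferroni rejection is lost.

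**4. Error control.** Let m0 nulls be true. When Holm first rejects a true null, at most m − m0 hypotheses have been rejected before it, so the threshold is at most 0.05/m0. The chance that any of the m0 true nulls has a P value that small is at most m0 × 0.05/m0 = 0.05, whatever the dependence.

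**5. Power under Bonferroni.** Tests are taken as two-sided, which the plan implies for opioid use ("whether or not the relative risk is different from a value of 1.0") but does not state generally. The documents give no secondary power, so I assume unadjusted power of 50%, 80% or 90% at 0.05, equal across real effects. The expected z-statistic is 1.960 + z(power), and the critical value at 0.05/7 two-sided is 2.690. Ignoring the negligible far tail:

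- 50%: Φ(1.960 + 0 − 2.690) = Φ(−0.73) = 0.23
- 80%: Φ(1.960 + 0.842 − 2.690) = Φ(0.11) = 0.54
- 90%: Φ(1.960 + 1.282 − 2.690) = Φ(0.55) = 0.71

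**6. Power under Holm.** This comes from simulating seven equicorrelated z-statistics, with at least 200,000 replicates per scenario and correlation 0 and 0.5 (also an assumption). The table shows average power per real effect:

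| Real effects of 7 | Unadjusted power | Bonferroni | Holm |
|---|---|---|---|
| 6 | 50% | 23% | 26-27% |
| 6 | 80% | 54% | 62-63% |
| 6 | 90% | 71% | 79-80% |
| 4 | 50% | 23% | 25% |
| 4 | 80% | 54% | 58% |
| 4 | 90% | 71% | 75% |
| 1 | 50-90% | 23-71% | same to within 0.1 point |

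With six real and 80% unadjusted power, the chance of showing all six rises from 3-18% to 12-34%. In no replicate did Holm miss a Bonferroni rejection, and Holm's family-wise error never exceeded 0.05.

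**7. At least one finding.** Both rules reject something exactly when the smallest P value is at most 0.05/m. The chance of at least one rejection is therefore identical.

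**8. Other family sizes (80% unadjusted power).** With m = 6 and all six real, power goes from 56% to 67-68%. With m = 19 and correlation 0.5, it goes from 42% to 49% with 16 real effects and from 42% to 43% with four.

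**The case against.** The strongest reply is that nothing is wrong. Bonferroni is valid, delivers the control the plan promises, and matches the method used for the primary outcome; the same remark fits any plan that uses it. It also has simple matching simultaneous intervals at level 1 − 0.05/m, and a team may reasonably want those. All of this stands, which is why the point is an improvement only. The loss of matching intervals is modest here, because for secondary outcomes the plan promises intervals only for the incidence of each complication.

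A second reply is that the gain depends on power values the documents do not give. That also stands. Equal power for continuous scales and for possibly rare events is a simplification, and at 50% unadjusted power the gain is only about 2 to 4 points with six real effects.

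A reader might infer more than the documents support:

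- *All seven effects are real.* That would raise power from 54% to 65-66% (80% unadjusted power). But the secondary hypothesis expects no additional adverse events at 90°C, so six is the most that the plan's own hypothesis supports.
- *The gain comes from the outcomes being correlated.* Holm does not use correlation; its gain comes from the number of false nulls. With seven real effects at 80% power, the gain falls from about 12 points at correlation 0 to about 9 at 0.8.
- *Each outcome is held to 0.0071 by the plan.* No count or level is stated.

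The interim looks are no obstacle to Holm. The boundaries are given with the primary analysis, and the group-sequential sample size rests on pain relief alone; none are given for secondary outcomes.

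**Conclusion.** The point holds as an optional gain in efficiency. That Holm keeps the same 5% control and never rejects less is a mathematical fact and needs no assumption about this trial. The size does: for a family of seven with six real effects and correlation 0 to 0.5, the gain is about 2 to 4 points of power per outcome at 50% unadjusted power and about 8 to 9 at 80-90%. It is about 1 to 4 points if four effects are real and nil if only one is. A reader might conclude that the present rule fails to control error or invalidates the secondary analyses; it does neither. The undefined family is a gap under either method, because both need m fixed in advance.

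**What to change.** Before any unblinded secondary data are seen:

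1. In the sentence on secondary type I error, replace the Bonferroni correction with the Holm step-down procedure at a family-wise 5%.
2. List the hypotheses in the family, and say whether the composite complication test and the by-visit tests that follow an interaction belong to it.
3. Report Holm-adjusted P values, with 95% confidence intervals labelled as unadjusted.

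This is a few lines of text. The sample size (216, or 237 with interim analyses), data collection and models do not change. The downside should be stated in the plan: Holm has no simple matching simultaneous intervals, so an unadjusted interval may exclude no effect beside a non-significant adjusted P value. If the team prefers matching intervals, keeping Bonferroni is defensible, but step 2 is still needed.

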- d. Subjects with bleeding disorders or active anticoagulation that cannot be stopped for few days close to the time of the procedure.
- e. Subjects who have an active systemic or local infection.
- f. Presence of radicular pain extending below the knee.
- g. Patients who have other specific etiology of low back pain (e.g. significant spinal canal stenosis or grade 2 or 3 spondylolisthesis).
- h. Secondary gain (i.e., ongoing litigation, worker's compensation or other financial incentives).
- i. Psychopathology including uncontrolled depression, somatization or poor coping skills.
- j. Physical factors including non-sedentary lifestyle, e.g.; morbid obesity (BMI >35kg/m²).
- k. History of previous RFA at the same level(s) in the previous 6 months.

Subject Withdrawal:

Subjects may voluntarily withdraw from the study at any time. Reasons for withdrawal will be recorded on the appropriate case report form (CRF). Pertinent data from such patients (either before or after the withdrawal) will be included in analysis if available, unless the patient explicitly states that they do not want their data to be included.

Terminating Subject Participation:

A subject's participation in the study may be terminated if continued participation in the study is not in the subject's best interest, in the investigator's opinion.

Methods:

• Study design:

This will be a prospective, randomized double-blinded study.

• Randomization:

After Institutional Review Board (IRB) approval and written consent, eligible patients, consenting to participate in the study will be randomly assigned to one of the two study groups (80°C or 90°C) based on computer-generated allocations which will be done immediately before use.

• Blinding:

Patient, physician performing the procedure and physician or research fellow assessing the outcomes will be blinded to the group assignment.

• Study Protocol:

Patients must meet all inclusion and exclusion criteria to be eligible for the study. After eligibility is confirmed, the patients will receive complete information about the study both verbally and in writing. Informed consent must be obtained from the patients prior to randomization and study-specific procedures. Once all eligibility criteria are fulfilled (including informed consent), the patients will be randomized, and treatment allocation will be performed. Key baseline patients characteristics, as well as patient's eligibility criteria, will be collected on case report forms.

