Randomization will be done through an independent study coordinator or research fellow other than the one who is assessing the outcomes. Patients will be randomly assigned to one of the two groups as 1:1 ratio.

The nurse who is responsible for operating the radiofrequency generator will be the only one informed about the randomization results through the unblinded study coordinator. The physician and the patient will both be blinded.

Intravenous access will be inserted for all patients and mild sedation with midazolam will be given according to the patient needs.

With the C-arm guidance a 20-gauge radiofrequency needles with 10mm active tips will be used to ablate 3-4 lumbar facet medial branches.

At each level, needles will be adjusted to optimize sensory and motor stimulation. For each nerve lesion, correct placement is confirmed using electrostimulation at 50Hz, with concordant sensation achieved at 0.5V or less. Before denervation, multifidus stimulation and the absence of leg muscles contractions is verified with electrostimulation at 2Hz.

The radiofrequency lesions will then be carried out at 80°C (group 1) or

90°C (group 2) for 90 seconds twice to produce the desired lesions of the medial branches.

• Data Collection:

Study data for follow-up visits will be collected by one of 3 ways. The follow-up visit questionnaires can be filled in-person, sent out to patients by mail or completed over the phone, whichever is more convenient for the patient.

Collected data will then be inputted and managed using REDCap (Research Electronic Data Capture) tools hosted at Cleveland Clinic. REDCap is a secure, web-based application designed to support data capture for research studies, providing:

1) An intuitive interface for validated data entry.

2) Audit trails for tracking data manipulation and export procedures.

3) Automated export procedures for seamless data downloads to common statistical packages.

4) Procedures for importing data from external sources.

• Patient Demographics:

- Age
- Sex
- Smoking
- BMI
- History of back surgeries.

Page ${\bf 9}$ of ${\bf 16}$

Protocol Version 3 Revision Date: 10/15/2019

- Diabetes mellitus.
- Response to diagnostic blocks

• Patient Baseline data:

- Preoperative and baseline pain score will be collected using Visual Analog Scale (VAS)
- Pain Questionnaires:
 - Pain Disability Index (PDI).
 - McGill Pain Questionnaire.
 - Beck Inventory (BI)
- Oral pain medications in morphine sulfate equivalent mg/day.

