Sample size estimation is based on the frequency distribution estimated across four categories of pain relief used in our preliminary retrospective study. Thus, for these calculations 38%, 9%, 37%, and 16% of patients undergoing RFA at 80°C are assumed to develop no improvement (=0%), minimal improvement (<25%), moderate improvement (25-75%), and marked improvement (>75%) in symptoms, respectively. We further assumed that the data was uniformly distributed across each category through simulation, and performed power calculations on the simulated data using categories of percent pain relief of 0, 1-10, 11-20, 21-30, \dots , 91 – 100. In order to have 90% power at the 0.0125 significance level at each time point (0.05/4 = 0.0125 at each time point) to detect a clinically significant shift in improvement of absolute 15% between RFA at 90°C and RFA at 80°C, a maximum of N=216 total patients would be required. Below we list the proportion of patients in each percent pain relief category as assumed for the sample size calculations described above. Although a 20% increase is in general what would be considered a clinically important improvement in pain relief, we plan for 15% since there may be a nontrivial fraction of patients who experience no relief in either group. Adjusting for 3 interim analyses and a final analysis would require a maximum of N=237. With the above parameters, there will be a cumulative 8%, 37%, 75%, and 100% chance of crossing a boundary at the 1st through 4th analyses if the alternative hypothesis is true as stated above.

Group	0	1-10	11-20	21-30	31-40	41-50	51-60	61-70	71-80	81-90	91-100
Control	.38	.041	.035	.06	.07	.067	.069	.087	.062	.057	.072
Experimental	0	0	.399	.041	.03	.083	.068	.064	.077	.078	.16

We plan to re-estimate sample size after obtaining at least 1 and 3 month continuous pain relief outcome for the first 60 patients, using the observed shape of the distribution and the variability of the outcome, but still based on an absolute 15 percent upward shift from the 80 degrees group. Type I error will be controlled using the methods in Kieser 2000 (9).

We will provide results to the Data and Safety Committee on efficacy and safety assessments, including conditional power analyses, but the committee will have final say on whether the study would progress to the next interim analysis or be stopped.

References

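### The sample sizes of 216 and 237 contain no allowance for loss to follow-up, so at the 0.0125 level the 90% power holds only where outcome data at the visit are essentially complete

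*Combined protocol and SAP*

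**What the plan says.** The section on sample size considerations sets its target as "In order to have 90% power at the 0.0125 significance level at each time point", with the effect defined as "to detect a clinically significant shift in improvement of absolute 15% between RFA at 90°C and RFA at 80°C". It concludes that "a maximum of N=216 total patients would be required". The next adjustment is for the group sequential design alone: "Adjusting for 3 interim analyses and a final analysis would require a maximum of N=237". The Interim analyses paragraph then places the looks at successive quarters of maximum enrolment, so 237 is an enrolment figure.

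Under Data Analysis (Primary Hypothesis), each of the 1, 3, 6 and 12 month visits is tested separately for whether the groups "differ with respect to the percentage of pain relief using the Wilcoxon rank-sum test". No missing-data method is given for that outcome. Under Subject Withdrawal, "Subjects may voluntarily withdraw from the study at any time", and data from such patients are used where they exist.

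The planned re-estimation is triggered by 1 and 3 month outcomes in the first 60 patients. Its stated inputs are the shape and variability of the outcome. No section states a loss rate or an inflation for loss.

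**The concern.** A rank-sum test at 12 months uses only patients who have a 12-month value. If the planned number is just enough when everyone contributes, every missing value is paid for in power at that visit. The plan foresees withdrawal and has a one-year horizon, but its arithmetic leaves no room for missing values.

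What is at stake is how a null result is read. A non-significant 12-month comparison would be reported as coming from a 90%-power test at 0.0125, when the power could have been several points lower. The re-estimation step would not catch this as written, because loss is not one of its inputs.

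**Working it through.** **Inputs.** Two-sided 0.0125 per visit and 90% power (sample size section). Sidedness is not stated, but the hypothesis is worded as a difference and only the two-sided level reproduces 216. Allocation: "Patients will be randomly assigned to one of the two groups as 1:1 ratio". Outcome distributions: the 11-category table, introduced with "Below we list the proportion of patients in each percent pain relief category as assumed for the sample size calculations described above"; each row sums to 1.000. Spending functions: gamma −4 (efficacy) and −2 (futility), four looks.

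**Step 1: effect size.** From the table, P(90°C better) = 0.6201 and P(tie) = 0.0551, so p = 0.6201 + 0.5 × 0.0551 = 0.6477.

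**Step 2: reproduce 216.** Noether's formula for the rank-sum test with equal groups is N = (z₁₋α/₂ + z_power)² / [3(p − 0.5)²].
- z values: 2.498 + 1.282 = 3.779; squared, 14.28.
- N = 14.28 / (3 × 0.1477²) = 218.4, or 213.8 with the tie correction (factor 0.979).
- The stated 216 lies between the two. One-sided 0.0125 gives 186–190 and two-sided 0.05 gives 157–161; neither fits.

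No loss term is needed to reach 216.

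**Step 3: reproduce 237.** With the printed boundaries (overall two-sided 0.05), numerical integration gives an inflation of 1.094, and 216 × 1.094 = 236.4. The cumulative chances of crossing a boundary come out at 8%, 37%, 75% and 100%, as printed. With boundaries rebuilt to spend 0.0125, the inflation is 1.081, so the number needed is 1.081 × 213.8 to 218.4 = 231 to 236. Either way the extra 21 patients are the cost of the looks. At 0.0125 the slack is 237 − 236 = 1 to 237 − 231 = 6 patients.

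**Step 4: power with loss.** With N patients who have the outcome, the drift is √(3N) × (p − 0.5), divided by √0.979 for the tie-corrected version. Set N = 237 × (1 − loss). Ranges are without and with the tie correction.

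| Assumed missing at the visit | Patients with outcome | Power, boundaries spending 0.0125 | Power, boundaries as printed (0.05) |
|---|---|---|---|
| none | 237 | 90.1–90.8% | about 96% |
| 1 patient | 236 | 90.0–90.7% | about 96% |
| 5% | 225 | 88.4–89.1% | 95.5–95.8% |
| 10% | 213 | 86.4–87.2% | 94.5–94.9% |
| 15% | 201 | 84.1–84.9% | 93.4–93.8% |
| 20% | 190 | 81.4–82.3% | 92.0–92.5% |
| 25% | 178 | 78.4–79.4% | 90.3–90.9% |

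Hand check at 20%: 189.6 / 1.081 = 175.5 fixed-design equivalents; √(3 × 175.5) × 0.1477 − 2.498 = 0.89; Φ(0.89) = 81.3%.

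Two conventions apply. The loss rates are assumptions, and only lost information is counted, not bias from informative dropout. The last-look futility limit is printed as 0.0040 beside an efficacy limit of 0.0440, so the two regions overlap. The printed-boundary column uses 0.0440 for both, the value with which the design reproduces.

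**The case against.** The strongest counter-argument is that the shortfall depends on an alpha that the printed boundaries do not use. On those boundaries, power stays at or above 90% throughout the 5–25% range. That stands as a limit on the conclusion. It does not rescue the claim, because the plan makes its 90% statement at 0.0125, and the additional power comes from testing each of four visits at 0.05, which gives up the stated Bonferroni control.

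A reader might infer that the stated power fails as soon as one patient is lost. It does not: one lost patient costs about 0.1 point, and 5% loss leaves power within 2 points of 90%.

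A reader might also infer that substantial loss is expected, citing the amendments that allow mail or telephone completion. The documents do not support this. Remote completion is a way of keeping data, subjects who decline follow-up are excluded, and a withdrawn patient may still supply data. No loss rate can be drawn from these provisions, though none of them is an allowance in the sample size either.

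Finally, the plan powers for 15 points while describing 20 as what would generally be clinically important. For a 20-point shift applied to the control distribution (Noether approximation, 0.0125, same categories), power is about 95%, 93% and 89% with 0%, 10% and 20% missing. This softens the practical consequence, but the plan's 90% is stated for 15 points. The re-estimation makes 237 provisional, but not with respect to loss.

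**Conclusion.** The point holds in a limited form. The figures of 216 and 237 count patients with an outcome at the visit tested and are used as enrolment. At the stated 0.0125 level and the tabulated 15-point shift, 90% power requires essentially complete data at the visit. Under assumed losses of 5%, 10%, 15% and 20%, power at that visit is about 89%, 87%, 84–85% and 82%.

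The effect is confined to visits where values are missing: loss at 12 months does not lower power at visits whose data are complete. The documents do not support a flat statement that the 12-month comparison is underpowered, since the loss rate is unknown and the alpha in force is unsettled between the 0.0125 criterion and boundaries that spend 0.05 overall.

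**What to change.** 1. State that 90% power refers to 237 patients with the outcome at the visit tested, and give power over a range of losses labelled as assumed, such as the 5–20% rows above.
2. Reconcile the 0.0125 criterion with the printed boundaries, and name in the power statement the alpha it uses. If the printed boundaries were kept, the power figures would change as in the last column of the table.
3. Add observed loss to follow-up as an input to the re-estimation at 60 patients, noting that 1 and 3 month data may understate loss at 12 months.

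The cost is a few sentences and a somewhat less favourable stated power at 12 months. The restatement adds no patients. Enrolling more to hold 90% would be a separate decision: 237 / 0.90 gives 264 at 10% loss and 237 / 0.80 gives 297 at 20%, both on assumed rates.
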